At the beginning of the first in-person session and at the end of the second in-person session, for both the RPCW active intervention and the HEC condition, three standardized instruments will be administered to participants. **Participants will be seated a minimum of 6 feet apart in the group session room and administered these instruments on an individual laptop with earphones to allow them privacy.** These include the Video Vignette Risk Perception Measure (VVRPM) which assesses women's standardized ability to assess sexual assault risk cues. The Adult Faces test from the Diagnostic Analysis of Nonverbal Accuracy 2 (DANVA2) which is used to measure an individual's general ability to sensitivity to perceive nonverbal cues, and the sDERS a measure used to assess state emotion regulation (assessed using a web-based platform as are the other survey measures for the study). All data will be uploaded off of these laptops and saved to the project UB Box at the end of each in-person session.

Outlines for the in-person RPCW and HEC sessions are attached and links to the on-line learning units for both the RPCW and HEC are included for review.

10.2 Describe what data will be collected.

NOTE: For studies with multiple data collection points or long-term follow up, consider the addition of a schedule or table in your response.

Response:

Study 2:

Participants will participate in the intervention over about one week. They will attend two in-person group intervention sessions about one week apart, and complete two on-line units during the intervening week. They will be asked to complete follow-up on-line assessment surveys at 3 months and 6 months post intervention.

The follow-up surveys will be administered online and are included for review.

 *10.3 List any instruments or measurement tools used to collect data (e.g. questionnaire, interview guide, validated instrument, data collection form).*

Include copies of these documents with your submission.

Response:

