17.0 Data Management and Analysis

17.1 Describe the data analysis plan, including any statistical procedures. This section applies to both quantitative and qualitative analysis.

Study 2:

Data Analyses

For the RCT, data will be analyzed according to the intention-to-treat principle [122]. All participants who complete the baseline assessment will be followed (i.e., post-intervention, 3-month and 6-month post-intervention) regardless of treatment participation. Given our experience and past record of retaining participants in longitudinal studies and the relatively brief period of follow-up (6-mos), dropout due to attrition is expected to be low. We anticipate no more than 5% of data will be missing through attrition or wave nonresponse (i.e., not completing all measures at a given time period). To adjust for any missing assessments, we will use multiple imputation procedures [123, 124].

We have three specific hypotheses for the RCT, our analyses are organized below for each hypothesis.

Hypothesis a: Participants in the RPCW intervention will report fewer days of hazardous drinking and improved perception of SRV risk cues on the video risk perception measure (primary outcomes) as compared with participants in the HEC condition.

Differences in relevant outcome variables (e.g., number of heavy drinking days, perception of SRV risk cues) will be tested using a 2 (Condition: RPCW vs. HEC) x 4 (Time: baseline, post-treatment, and 3- and 6-month post-treatment) repeated-measures analysis of variance (RM-ANOVA). The primary effects of interest are the intervention condition main effect and the intervention x time interaction. If a significant condition by time interaction is found, it means that (a) change over time in heavy drinking days differs across intervention conditions and (b) the effect of intervention condition on the outcome is different across time. Therefore, a significant intervention condition by time interaction will be explored by computing the conditional effect of time for each intervention condition and (b) the conditional effect of treatment condition at each of the four time points.

Hypothesis b: Participants in the RPCW intervention will report increased knowledge of safe dating practices and protective behavioral (drinking) strategies (secondary outcomes) compared with participants in the HEC condition.

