Differences in relevant outcome variables (e.g., safe dating practices, protective behavioral drinking strategies) will be tested using the same 2 (Condition) x 4 (Time) repeated-measures analysis of variance (RM-ANOVA) described above for hypothesis a.

Hypothesis c: Participants in the RPCW intervention will report lower rates of SRV as compared with participants in the HEC condition at 6-month post-intervention follow-up.

Given that SRV has a low base rate of occurrence, we consider this hypothesis exploratory and will conduct a preliminary comparison of the incidence of SRV at 3-months and 6-months post-treatment across the RPCW and HEC conditions using a chi-square test.

Effect sizes will be calculated with all analyses in preparation for a Stage II efficacy trial of the intervention.

17.2 If applicable, provide a power analysis.

NOTE: This may not apply to certain types of studies, including chart/records reviews, survey studies, or observational studies. This question is asked to elicit whether the investigator has an adequate sample size to achieve the study objectives and justify a conclusion.

Response:

Study 2:

The sample size of 96 women (48 women per intervention condition) was selected to provide 80% power to detect at least medium effect sizes in RM-ANOVA. For Hypotheses a and b, power calculations were conducted for a 2 (treatment condition) x 4 (time) RM-ANOVA. We calculated power using the following assumptions (1) a sample size of 48 women in each intervention condition (RPCW, HEC), (2) 4 time points for assessment (baseline, post-intervention, and 3- and 6-months post-intervention), (3) a range of correlation values among repeated assessments ($r = .3$ to $.9$), (4) no violation of the sphericity assumption, (5) $\alpha = .05$, two-tailed, and (6) power = 80%. Based on these assumptions, there is 80% power to detect an intervention condition main effect with medium effect sizes ($f = .20$ to $.28$) and both a time main effect and an intervention condition x time interaction with small to medium effect sizes ($f = .05$ to $.21$). For Hypothesis c, statistical power was estimated for a χ^2 test (1 df) of the number of women who were and were not revictimized post treatment by intervention condition (RPCW, HEC). Assuming (1) a total sample of 96 women, (2) $\alpha = .05$, and (3) 80% power, the chi-square analysis can detect a medium effect ($w = .29$) at 3- and 6-month post-intervention.

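### No sphericity correction is specified for the four-visit RM-ANOVA, so the condition x time test for hazardous drinking days is probably mildly liberal (about 5.4-7% at a nominal 5%)

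*Protocol*

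**What the plan says.** Protocol 17.1 and the SAP (Data Analyses) specify, for Hypothesis a, a "2 (Condition: RPCW vs. HEC) x 4 (Time: baseline, post-treatment, and 3- and 6-month post-treatment) repeated-measures analysis of variance (RM-ANOVA"). The same model is reused for the secondary outcomes under Hypothesis b. On what will be tested, 17.1 states: "The primary effects of interest are the intervention condition main effect and the intervention x time interaction". A significant interaction is to be followed by effects of time within each condition and effects of condition at each visit. No error term is named for these contrasts.

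The only mention of sphericity is in the power text (Protocol 17.2 and SAP, Power), where one assumption is "no violation of the sphericity assumption". Neither document names an epsilon correction, a multivariate test or a mixed model.

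On timing, Protocol 10.2 says of participants: "They will attend two in-person group intervention sessions about one week apart". The baseline and post-intervention measures belong to those two sessions. The remaining surveys come three and six months after the intervention.

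**The concern.** The within-subject F test in RM-ANOVA has its nominal size only if the differences between every pair of visits have the same variance (sphericity). With equal variances at each visit, that means baseline must correlate with a measure one week later no more strongly than with one half a year later. This is hard to defend for a count of drinking days. When the assumption fails, the F statistic is referred to too many degrees of freedom and rejects too often.

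The interaction is one of two effects named as primary. A falsely significant interaction would also trigger the planned follow-up contrasts, and the pilot is meant to inform a Stage II trial. Leaving the correction unstated also leaves the choice of p-value open until the data have been seen.

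**Working it through.** **Inputs from the documents.** 48 women per arm, N = 96, so 94 between-subject df. Four visits, so the interaction has 3 df and its error term 3 x 94 = 282. Alpha .05. Correlations .3 to .9, with no pattern over time (Protocol 17.2; SAP, Power). Visits at about weeks 0, 1, 14 and 27 (Protocol 10.2, taking three months as 13 weeks).

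**Assumed.** Equal variances across visits, and the correlation patterns in the table.

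**Step 1: the plan's own figures.**
- Main effect: noncentrality N f² m / [1 + (m - 1) r] on 1 and 94 df gives f = .199 at r = .3 and .278 at r = .9. This reproduces .20 to .28.
- Interaction under sphericity: noncentrality N f² m / (1 - r) on 3 and 282 df gives f = .054 at r = .9, which rounds to the printed .05. At r = .3 it gives .142, not the printed .21.
- The .21 reappears only if noncentrality and both df are multiplied by the lower-bound epsilon of 1/3 (f = .209). The power text should be reconciled on this, but nothing below depends on it.

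**Step 2: size of the uncorrected test.** Let l1, l2, l3 be the eigenvalues of the covariance of three orthonormal time contrasts. Then

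epsilon = (l1 + l2 + l3)² / [3 (l1² + l2² + l3²)].

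Under the null, F is distributed as [sum of li x chi-square(1) / 3] / [sum of li x chi-square(94) / 282]. It is compared with the 5% point of F(3, 282), which is 2.64. Rejection rates were simulated with several hundred thousand draws per pattern.

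Worked example: baseline-post .9, pairs about three months apart .6, pairs about six months apart .4. The eigenvalues are .10, .35 and .80. Their sum is 1.25 and its square 1.5625. The sum of squares is .01 + .1225 + .64 = .7725. Epsilon = 1.5625 / (3 x .7725) = .674.

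| Baseline-post / 3 months apart / 6 months apart | Epsilon | Type I error |
|---|---|---|
| Equal correlation | 1.00 | 5.0% |
| .7 / .6 / .5 | .93 | 5.4% |
| .8 / .5 / .4 | .81 | 6.1% |
| .9 / .3 / .3 | .72 | about 7% |
| .9 / .6 / .4 | .67 | 7.0% |
| Exponential decay, .6 per 13 weeks | .59 | 7.8% |
| Exponential decay, .7 per 13 weeks | .57 | 7.8% |

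The two decay rows imply baseline-post correlations of .6^(1/13) = .96 and .7^(1/13) = .97. Both lie outside the plan's range. As a wider check, 2,000 random matrices within .3 to .9, with correlation falling with lag, gave a median of 6.5% (5th to 95th percentile 5.2-7.9%). A stable person effect plus measurement error gave 5.1-6.6%.

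**Step 3: with the correction.** Multiplying both df by the true epsilon brings the error to 4.8-5.0% in every row.

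**Step 4: follow-up contrasts, if they used the pooled within-subject error.** In the .9 / .6 / .4 pattern the pooled variance of a difference is 2 x 1.25/3 = .833.
- Baseline to six months: true variance 2(1 - .4) = 1.20, which is 1.44 times the pooled value. The effective critical value is 1.968/√1.44 = 1.64, so the test rejects about 10% of the time.
- Baseline to post: true variance 2(1 - .9) = .20, or .24 of the pooled value. This contrast is extremely conservative.

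**The case against.** **The size is conditional.** The documents give a range of correlations and no pattern. Uneven spacing does not by itself break sphericity, which is also a weaker condition than equal correlation. The flatter .7 / .6 / .5 pattern costs only 0.4 of a point. This stands: the 5.4-7% describes plausible patterns and is not a property that can be read from the plan.

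**The four-visit structure may not apply.** Protocol 10.3 links drinking most directly to the three- and six-month surveys and describes the post-intervention survey mainly through its satisfaction questionnaire. If drinking were analysed at baseline, three and six months only, the one-week pair would drop out. Similar decay would then give epsilon of about .88-.93 and an error of 5.3-5.5%. However, 17.1 plans four time points, and the figures above take it at its word.

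**Multiple imputation.** A reader might infer that RM-ANOVA cannot be combined with the planned imputation. The documents do not support that. Multi-parameter pooling rules exist, and expected missingness is at most 5%. All that can be said is that the plan does not state how the interaction test will be pooled.

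**This is a pilot.** Its main outputs are feasibility, acceptability, safety and effect sizes, and an epsilon correction leaves effect estimates unchanged. That limits the weight of the point. It does not remove it, because the plan also tests the interaction for significance as a primary effect.

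**Conclusion.** The point holds as a modest, inexpensive improvement. Run as written and without correction, the interaction test for hazardous drinking days is probably mildly liberal: about 5.4-7% for plausible patterns within the plan's range, and up to about 8% under steeper decay. The same applies to any secondary outcome measured at all four visits. This rests on correlation falling with time, equal variances, and drinking being measured at all four visits. If sphericity holds, the error is 5%.

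Three stronger readings are tempting but unsupported:
- A reader might infer that the plan has decided against a correction. It is silent, and sphericity appears only as a power assumption.
- A reader might infer that sphericity must fail by design. It is likely to fail, but nothing in the documents establishes this.
- A reader might infer that the whole primary analysis is affected. The condition main effect is a between-subject test and is untouched. Protocol 10.1 and 10.3 schedule the video risk-perception measure only at the two in-person sessions, and with two time points sphericity cannot fail.

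The inflation of follow-up contrasts is likewise conditional, because no error term is specified.

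**What to change.** In Protocol 17.1 and the SAP, state that p-values for time and condition x time use Greenhouse-Geisser-corrected degrees of freedom whenever more than two visits are analysed. State also that follow-up contrasts use visit-specific error and not the pooled within-subject term. Alternatively, and to the same end, fit a mixed model with visit as a category and an unstructured covariance, using all observed visits. That also avoids having to pool the RM-ANOVA interaction test over imputations.

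Either route needs only a few sentences and standard software, with no change to design or sample size. The cost is a slightly less favourable interaction test. In the .9 / .6 / .4 pattern the df fall to 3 x .674 = 2.02 and 282 x .674 = 190, and the critical value rises from 2.64 to 3.03. On the Step 1 formula, with noncentrality and both df multiplied by epsilon, the effect detectable with 80% power at r = .3 goes from f = .142 to .157 at epsilon .75 and .170 at epsilon .60. Both are still below the plan's printed upper figure of .21.

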6.0 Inclusion and Exclusion Criteria

- 6.1 *Describe the criteria that define who will be **included** in your final study sample.*

NOTE: This may be done in bullet point fashion.

Response:

Study 2:

Eligibility Criteria. Inclusion criteria are: (1) 18-22 years of age, (2) female currently enrolled at the University at Buffalo in an undergraduate program, (3)

able to comprehend the study protocol, consent form and provide written consent, (4) have had a prior SA experienced since the age of 14 years (i.e., adolescent or young adult), and (5) have engaged in hazardous drinking in the past month (i.e., ≥ 4 drinks one or more times in the past 30 days).

We are recruiting women 18-22 years of age who are currently enrolled at the University at Buffalo. Given that HD has been associated with SA, we are incorporating reduction of HD into our intervention; therefore, we include women with a history of drinking or HD.

6.2 Describe the criteria that define who will be *excluded* from your final study sample.

NOTE: This may be done in bullet point fashion.

Response:

Study 2:

Exclusion criteria are: (1) Major mental illness as indicated by: (a) severe level of depressive symptoms as assessed by the BDI-II (a score greater than 30) or a self-reported diagnosis of: (b) Schizophrenia, (c) Bipolar Disorder; (2) unable to commit to attending 2 in-person group sessions, approximately one week apart (3) no access to a computer to complete the on-line intervention modules, and (4) currently being in another research study designed to reduce drinking/alcohol consumption and/or sexual victimization.

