10.0 Procedures Involved

*10.1 Provide a description of **all research procedures or activities** being performed and when they are performed once a subject is screened and determined to be eligible. Provide as much detail as possible.*

NOTE: This should serve as a blueprint for your study and include enough detail so that another investigator could pick up your protocol and replicate the research. For studies that have multiple or complex visits or procedures, consider the addition of a schedule of events table in in your response.

Response:

Study 2:

During the Stage 1b Randomized Controlled Trial of the active intervention, the first group session will focus on viewing each of 4 cue recognition training videos and the Interventionist will lead a discussion intended to highlight the risk cues in each of the videos. After the session, links and passwords will be sent via email to each participant for the online safe dating and safe drinking learning modules and participants will be asked to complete them prior to the second group session, which will take place about one week after the first session. This second group session will elicit feedback on the dating and drinking learning modules (e.g., length, ease of use, engagement, interest). The training videos will be viewed again individually and participants will engage in behavioral skills rehearsal of appropriate responses in paired role plays with feedback from the PI and Interventionist. During the behavioral rehearsal segment, the PI or Interventionist will engage the group in a discussion of emotional barriers to engaging in appropriate dating and drinking safety behaviors (e.g., "I feel bad for the guy", "He might get really mad, "I might miss out on being with a great guy") and strategies for overcoming these barriers. Adaptive emotion regulation strategies will include cognitive reappraisal, distress tolerance, mindfulness of current emotions, acceptance, and problem solving. Immediately following this session, the post-intervention measures, including feedback on the intervention content and process, will be completed. Following the in-person RPCW sessions, a debriefing will occur to ensure that women have an opportunity to discuss any emotional discomfort or distress with the interventionist. Women will receive \$30 for completion of the post-intervention measures.

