Project Title: Assessing the Feasibility of a New Prevention to Reduce Alcohol-related Sexual Revictimization of College Women

NCT#: NCT05257603

Document Date: 07/02/2018

Statistical Design and Power

Data Analyses

For the RCT, data will be analyzed according to the intention-to-treat principle [122]. All participants who complete the baseline assessment will be followed (i.e., post-intervention, 3-month and 6-month post-intervention) regardless of treatment participation. Given our experience and past record of retaining participants in longitudinal studies and the relatively brief period of follow-up (6-mos), dropout due to attrition is expected to be low. We anticipate no more than 5% of data will be missing through attrition or wave nonresponse (i.e., not completing all measures at a given time period). To adjust for any missing assessments, we will use multiple imputation procedures [123, 124].

We have three specific hypotheses for the RCT, our analyses are organized below for each hypothesis.

Hypothesis a: Participants in the RPCW intervention will report fewer days of hazardous drinking and improved perception of SRV risk cues on the video risk perception measure (primary outcomes) as compared with participants in the HEC condition.

Differences in relevant outcome variables (e.g., number of heavy drinking days, perception of SRV risk cues) will be tested using a 2 (Condition: RPCW vs. HEC) x 4 (Time: baseline, post-treatment, and 3- and 6-month post-treatment) repeated-measures analysis of variance (RM-ANOVA). The primary effects of interest are the intervention condition main effect and the intervention x time interaction. If a significant condition by time interaction is found, it means that (a) change over time in heavy drinking days differs across intervention conditions and (b) the effect of intervention condition on the outcome is different across time. Therefore, a significant intervention condition by time interaction will be explored by computing the conditional effect of time for each intervention condition and (b) the conditional effect of treatment condition at each of the four time points.

Hypothesis b: Participants in the RPCW intervention will report increased knowledge of safe dating practices and protective behavioral (drinking) strategies (secondary outcomes) compared with participants in the HEC condition.

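### If heavy drinking days are asked at the post-treatment occasion, that occasion dilutes the condition main effect, because it is measured as session 2 ends; if they are not asked, the four-occasion model does not fit this outcome.

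*Protocol*

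**What the plan says.** Protocol 17.1 (Hypothesis a), repeated in the SAP under Data Analyses, puts both primary outcomes into one model: "Differences in relevant outcome variables (e.g., number of heavy drinking days, perception of SRV risk cues") are tested in a 2 x "4 (Time: baseline, post-treatment, and 3- and 6-month post-treatment) repeated-measures analysis of variance (RM-ANOVA". On what counts as the result: "The primary effects of interest are the intervention condition main effect and the intervention x time interaction". If the interaction is significant, the follow-up analyses include "the conditional effect of treatment condition at each of the four time points". Protocol 17.2 and the SAP's Power text rest on the same four occasions.

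Protocol 10.1 fixes when the second occasion happens, which is after the second group session: "Immediately following this session, the post-intervention measures, including feedback on the intervention content and process, will be completed". Protocol 10.2 gives the spacing: "They will attend two in-person group intervention sessions about one week apart, and complete two on-line units during the intervening week". Baseline is at the first group session (25.1) or shortly before it (26.2).

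Neither document states a recall window for heavy drinking days as an outcome. The 30-day period appears only where hazardous drinking is defined (3.0) and in eligibility (6.1): "have engaged in hazardous drinking in the past month (i.e., ≥ 4 drinks one or more times in the past 30 days"). Protocol 10.3, as worded, attaches the drinking outcome to the 3- and 6-month surveys. It describes the post-intervention survey only as including a satisfaction questionnaire.

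**The concern.** A count of heavy drinking days looks backwards. Taken as session 2 ends, it contains no day after the completed intervention, whatever the recall window. Role-play rehearsal and the discussion of emotional barriers take place in session 2 itself, and the online drinking module is done at some point in the week before. At best the count reflects a few days of partial exposure.

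The planned main effect nevertheless weights this occasion equally with 3 and 6 months. Protocol 1.1 says the pilot is to supply initial efficacy data for Stage II power calculations, and 17.1 asks for effect sizes from all analyses. A main-effect estimate that averages in an occasion close to a second baseline understates the follow-up effect for that purpose. The video and knowledge measures do not have this problem, because they are not look-back counts.

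**Working it through.** **Inputs from the documents.** 48 per arm; four occasions; correlation among occasions r = .3 to .9; two-sided alpha .05; sphericity (Protocol 17.2, SAP Power). Sessions about 7 days apart (10.2).

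**Assumptions.** An arm difference d = 0.5 SD at both 3 and 6 months, zero at baseline, and equal correlations between all occasions. Drinking is taken to be asked at the post-treatment occasion.

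**The plan's own figure.** For the main effect, λ = f²·N·m/(1+(m−1)r) with N = 96, m = 4, F(1, 94). Solving for 80% power gives f = .199 at r = .3 and .278 at r = .9, which reproduces the stated .20 to .28.

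**Share of the 3/6-month difference kept by the four-level main effect.**
- Post-treatment carries the full effect: (0+d+d+d)/4 = 0.75d.
- It carries none: (0+0+d+d)/4 = 0.50d.
- With a 30-day window (an assumption) and all 7 in-intervention days fully affected: (0+7/30+1+1)/4 = 0.558, so 56%.

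Of the drop from 100% to 50%, the first quarter comes from baseline being a Time level and the second from the post-treatment occasion.

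**Power of the four-level main effect.** λ = D²/[((1+3r)/4)(2/48)], F(1, 94), where D is the averaged difference. At r = .5 the variance is 0.625 × 2/48 = 0.02604. With no effect at post-treatment, λ = 0.25²/0.02604 = 2.40 and power is 34%. With the full effect there, λ = 0.375²/0.02604 = 5.40 and power is 63%.

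**Isolating the occasion from the baseline problem.** Make baseline a covariate and average k follow-up occasions. The variance is [(1+(k−1)r)/k − r²](2/48), F(1, 93). At r = .5:
- k = 3 (post-treatment, 3 and 6 months): estimate 2d/3 = 0.333, variance 0.01736, λ = 6.40, power 71%.
- k = 2 (3 and 6 months): estimate d = 0.5, variance 0.02083, λ = 12.0, power 93%.

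**Interaction.** λ = 24·SS/(1−r), where SS is the sum of squared deviations of the arm-difference profile from its mean. At r = .5:
- Profile (0, 0, d, d): SS = 0.25, λ = 12.0, F(3, 282), power 83%.
- Post-treatment dropped, baseline kept as a level, profile (0, d, d): SS = 0.167, λ = 8.0, F(2, 188), power 71%.

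| Analysis (d = 0.5) | Share of 3/6-month difference | Power, r = .3 | r = .5 | r = .7 |
|---|---|---|---|---|
| Main effect, 4 levels, full effect at post | 75% | 75% | 63% | 54% |
| Main effect, 4 levels, none at post | 50% | 42% | 34% | 28% |
| Baseline covariate; post, 3, 6 months; none at post | 67% | 68% | 71% | 83% |
| Same, 7/30 of the effect at post | 74% | 77% | 80% | 90% |
| Baseline covariate; 3 and 6 months only | 100% | 90% | 93% | 98% |
| Interaction, 4 levels, none at post | – | 68% | 83% | 97% |
| Interaction, post dropped, baseline kept as level | – | 55.5% | 71% | 91% |

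With d = 0.4 and 0.6 the direction is the same. At r = .5, four-level main-effect power falls from 45% to 23% and from 79% to 45% respectively when post-treatment carries none rather than all of the effect.

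**The case against.** Several points on the other side stand.

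- **Only one primary effect is affected.** A reader might infer that the primary drinking analysis as a whole is diluted. It is not: 17.1 names two primary effects, and an occasion with no effect acts as a second baseline, which raises interaction power when the effect is sustained at 3 and 6 months. The interaction does not, however, estimate the size of the follow-up effect.
- **The 50% is not all due to this occasion.** Half of that loss comes from treating baseline as a Time level. The comparison that isolates the post-treatment occasion uses a baseline covariate, which the plan does not propose.
- **The instruments are not in the documents.** It is tempting to say that 23 of the 30 days counted at post-treatment repeat the baseline window. That needs a 30-day outcome window, and the documents give 30 days only for the definition and for eligibility. Nor does the text confirm a drinking item in the post-intervention survey. Its absence would not rescue the plan, because the stated model and power basis would then lack one of their four occasions.
- **Equal correlations are a simplification.** If the baseline and post-treatment windows overlap, those two counts should correlate more strongly than the rest. The power figures are illustrative; the percentage shares do not depend on the correlations or on d.
- **The post-treatment contrast is not a false null.** A reader might infer that a near-zero result there would mislead Stage II on its own. It is computed only after a significant interaction, would be reported beside the 3- and 6-month contrasts, and would correctly describe that week. The averaged main effect is what misleads.

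This is also a pilot, no data are lost, and the 3- and 6-month contrasts remain recoverable. That bears on severity, not on whether the text needs changing.

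**Conclusion.** The point holds for the condition main effect and is a should-fix. The timing rests on the documents alone: under any recall window, no drinking day counted at the post-treatment occasion follows the completed intervention.

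The consequence depends on a fact the documents leave open. If drinking is asked at that occasion, the four-level main effect lies between 50% and 75% of the 3/6-month difference, according to how much effect the intervention week carries. With baseline as a covariate and no effect in that week, keeping the occasion still leaves a one-third underestimate; at r = .5 and d = 0.5 it costs 22 points of power (93% to 71%). If drinking is not asked, the 2 x 4 model and its power calculation cannot be applied to this primary outcome as written. Both branches call for the same correction.

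**What to change.** In Protocol 17.1 and the SAP:

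- Analyse heavy drinking days at 3 and 6 months, adjusted for baseline.
- State one recall window for this outcome and use the same window at baseline, 3 and 6 months.
- Keep the post-treatment occasion for the video and knowledge measures.
- If the post-intervention survey has a drinking item, report it descriptively as drinking during the intervention.
- In 17.2 and the SAP's Power text, restate the drinking calculation for two follow-up occasions with a baseline covariate.

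Do not simply delete the post-treatment level while leaving baseline as a Time level. That lowers interaction power (83% to 71% at r = .5, d = 0.5), and the main effect still recovers only two thirds of the difference.

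The cost is a wording change in the two documents and a short recalculation. No visit is added. The recall window should be checked against the existing surveys, whose wording would change only if the windows differ. The downside is that no drinking effect is tested before 3 months.
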